### 2.3.3 Assessment of Potential Risks and Benefits

Fostamatinib has a consistent safety profile and adverse events are clearly documented. Currently the only immunomodulating therapy that has proven benefit in patients with COVID-19 is dexamethasone which improved mortality from 24.6% to 21.6% (RR 0.80, 95% CI 0.74-0.92,  $p < 0.001$ ) when compared to usual care in patients with COVID-19. This improvement in mortality was more dramatic in patients who required mechanical ventilation where mortality improved from 40.7% to 29.0%, resulting in a need to treat 8 patients to show benefit in one. However, the high mortality rate in the control group compared to usual care in the United States, the multiple randomizations permitted, and lack of remdesivir as part of usual care make interpreting the results of this study for patients in the United States difficult. Furthermore, the mechanism of action by which dexamethasone would improve outcomes is not known as steroids have indiscriminate broad ranging effects on immunosuppression. Fostamatinib has many potential advantages over steroids including a targeted mechanism of action that inhibits multiple pathways in the pathogenesis of COVID-19 including decreasing Fc receptor signaling on neutrophils, monocytes and macrophages and CLEC receptors on neutrophils and platelets. Through these mechanisms we hypothesize that fostamatinib will decrease the immunodysregulation associated with COVID-19 along with the NETosis and inflammatory driven immunothrombosis that precedes much of the organ failure.

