## 3 OBJECTIVES AND ENDPOINTS

The primary objective of this study is to evaluate the safety of fostamatinib for the treatment of hospitalized patients with COVID-19.

OBJECTIVES	ENDPOINTS	JUSTIFICATION FOR ENDPOINTS
Primary		
To assess the safety of fostamatinib in hospitalized patients with COVID-19	Cumulative incidence of SAEs through day 29.	This endpoint was chosen to evaluate the safety of fostamatinib for the treatment of hospitalized patients with COVID-19.
Secondary		

*Abbreviated Title: Fostamatinib for COVID*

*Version Date: 09/17/2020*

OBJECTIVES	ENDPOINTS	JUSTIFICATION FOR ENDPOINTS

To assess the effect of fostamatinib on clinically relevant endpoints of disease course
	
 
1. Time to recovery by day 29: day of recovery is defined as the first day on which the subject satisfies one of the following three categories: Ordinal scale 3: hospitalized, not requiring supplemental oxygen-no longer requiring ongoing medical care; Ordinal scale 2: non-hospitalized, limitations on activities and/or requiring home oxygen; Ordinal scale 1: non-hospitalized, no limitations on activities
 
2. Number of days free of mechanical ventilation [patients with baseline ordinal scale 5-6 only]
 
3. Mortality at day 14 and 28
 
4. Grade 3 and 4 AE through day 60
 
5. Days of hospitalization
 
6. Ordinal scale at day 15 and day 29
 
7. Change in CRP, IL-6, ferritin, d-dimer, fibrinogen, absolute lymphocyte count, absolute neutrophil count, and platelet count from baseline [day 3, 5, 8, 11, 15, 29]
 
8. Number of days in the ICU [entire hospitalization]
 
9. Relative change in PaO2/FiO2 or SpO2/FiO2 ratio
 
10. Change in SOFA score from baseline (day 1) [day 3, 5, 8, 11, 15, 29]
 
11. Number of days on oxygen (Including nasal canula, HFNC, non-invasive, and mechanical ventilation)
 
12. Days free of renal failure [entire hospitalization]
 
	
Each of the secondary clinical endpoints were deemed to be clinically relevant indicates for improved or worsening disease course

*Abbreviated Title: Fostamatinib for COVID*

*Version Date: 09/17/2020*

OBJECTIVES	ENDPOINTS	JUSTIFICATION FOR ENDPOINTS

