	
 
a. Renal failure defined as               
 
i. Increase in serum creatinine by <math>\geq 0.3</math>mg/dL within 48 hours or
 
ii. Increase in serum creatinine by <math>\geq 1.5</math> times baseline which is known or presumed to have occurred within the prior seven days, or
 
 
 
13. Clinically relevant deep vein thrombosis (DVT) or pulmonary embolism (PE) [entire hospitalization]
 
	
Tertiary/Exploratory		

1) To study the host immunological response to COVID-19 and potential mechanism of action of fostamatinib.
	
As an exploratory endpoint we will study the immune mechanism by which fostamatinib improves outcomes in patients with COVID-19.
 
 
1. Characterization of plasma biomarkers of immune activation
 
2. Measure platelet-leukocyte aggregates
 
3. Measure leukocyte activation assays
 
4. Measure plasma cytokine and chemokine levels
 
5. Evaluate the coagulation cascade
 
6. Measurement of immune antigen-antibody complexes
 
7. Measure thromboelastography (TEG)
 
8. Measure biomarkers of endothelial dysfunction
 
9. Characterize leukocyte extracellular traps
 
10. SARS-CoV-2 viability via cell culture from oropharyngeal samples
 
	
These exploratory endpoints are relevant ex vivo and in vitro analysis that will help determine disease and mechanisms of action while on fostamatinib

OBJECTIVES	ENDPOINTS	JUSTIFICATION FOR ENDPOINTS
	11. Detection of viral antigen blood and oropharyngeal samples	

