## 4 STUDY DESIGN

### 4.1 OVERALL DESIGN

We intend to study fostamatinib for the treatment of hospitalized patients with COVID-19.

- This will be a multicenter, randomized, double-blind, placebo-controlled, phase 2 trial with the objective to evaluate the safety of fostamatinib compared to matching placebo in COVID-19 patients who are hospitalized with a 5, 6, or 7 on the 8-point ordinal scale.
- The NHLBI will be the Coordinating Center for this multicenter study. All participating sites will enroll and treat subjects as described below. Research labs for exploratory endpoints will be processed at participating sites or shipped to the NIH Clinical Center for processing.
- All study participants will receive standard of care throughout the entire study and then will be randomized to 150 mg of fostamatinib twice a day or placebo for 14 days (total 28 doses).
- Subjects will be assessed daily while hospitalized and followed until day 60. If patients improve and are discharged prior to day 14 the study drug will be continued until day 14 as an outpatient. Patients who are discharged on study drug will receive a phone call daily to assess for adverse events and will have safety labs drawn on days 3, 5, 8, 11 as applicable (outpatient third party lab acquisition may be utilized as needed). We will make every effort to bring back discharged patients for outpatient visits on days 15, 22, 29, and 60 to include laboratory draws. In patients who are unable to follow-up, they will receive a telephone visit as a follow up.
- Day 1 of study is the first day of study drug and patients will be followed until day 60.

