#### **6.1.1 Study Intervention Description**

Patients hospitalized with COVID-19 on oxygen will receive fostamatinib at a dose of 150 mg twice daily for 14 days or placebo. Patients who are discharged prior to completing a 14 day course will continue therapy as an outpatient.

Fostamatinib is a spleen tyrosine kinase inhibitor that is currently FDA approved for the treatment of thrombocytopenia in adult patients with chronic immune thrombocytopenia (ITP) who have had an insufficient response to a previous treatment.

The use of fostamatinib for the proposed indication is investigational and the study will be conducted under FDA IND #152131.

Fostamatinib is a prodrug with an active metabolite, R406, which is known to inhibit Fc-activating receptors and B-cell receptors. R406 is protein bound and has a half-life of 15 hours, with 80% of excretion occurring in feces and 20% excreted in urine.

Concomitant use with strong CYP3A4 inhibitors with fostamatinib will increase exposure to R406 that may result in increased risk of adverse reactions while concomitant use of strong CYP3A4 inducers reduces exposure to R406. Fostamatinib may increase the concentration of some CYP3A4 substrate drugs, some BCRP substrate drugs (ex. rosuvastatin), and some P-glycoprotein substrate drugs (eg. Digoxin).

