#### **8.4.4 Time Period and Frequency for Event Assessment and Follow-Up**

For this study, all grade 3 and 4 AE, clinically significant laboratory abnormalities, and all SAEs occurring from the time the informed consent is signed through the Day 60 visit will be documented, recorded, and reported in an NHLBI-approved research database. All other AEs will be collected in the subject's medical records.

The occurrence of an AE or SAE may come to the attention of study personnel during study visits and interviews of a study participant presenting for medical care, or upon review by a study monitor.

All reportable AEs including local and systemic reactions not meeting the criteria for SAEs will be captured on the appropriate CRF. Information to be collected includes event description, time of onset, clinician's assessment of severity, relationship to study product (assessed only by those with the training and authority to make a diagnosis), and time of resolution/stabilization of the event. All AEs occurring while on study must be documented appropriately regardless of relationship. All AEs will be followed to adequate resolution.

Any medical condition that is present at the time that the participant is screened and until participant receives the first dose of study drug will be considered as baseline and not reported as an AE. AE occurrence will be assessed as any change from baseline in any medical condition that results in worsening in severity and/or frequency of the medical condition, whether or not considered related to study medication.

Changes in the severity of an AE will be documented to allow an assessment of the duration of the event at each level of severity to be performed. AEs characterized as intermittent require documentation of onset and duration of each episode.

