#### **9.3.3 Analysis of the Secondary Endpoint(s)**

To determine a subject's clinical status using the ordinal scale: On Day 1, report their clinical status at enrollment (start of study drug). On Day 2, report the period from enrollment to midnight on Day 1. On Day 3 through Day 11, or until discharged, and on Days 15, 22 and 29, provide the worst clinical assessment for the previous day (i.e., midnight to midnight; 00:00 –

23:59 (24-hr clock)). For example, on study Day 3 when completing the form, the worse clinical outcome measure of Day 2 is captured with the worst being death followed by ECMO, mechanical ventilation, etc. The Day 2 measurement is assessed as occurring anytime in that 24-hour period (00:00 to 23:59).

Secondary endpoints will be evaluated as follows:

1) The time to recovery by Day 29, it will be estimated by median and 95% confidence interval by study arm. The cumulative recovery rate will be estimated by the Kaplan-Meier method. The comparison between two treatment arms will be assessed by the log-rank test. The recovery ratio and hazard ratios will be based on the Cox model. The analysis will be stratified by disease severity at enrollment.

The time to recovery will be evaluate and censored up until Day 29. It is defined as the elapsed time in days from the day 1 to the earliest day at which a subject reaches recovery (having 1-3 of the 8-point ordinal scale). Any subjects that are lost to follow-up prior to an observed recovery will be censored at the day of their last observed assessment. Subjects who complete follow-up but do not experience recovery will be censored at Day 29. All deaths within Day 29 (and prior to recovery) will be considered censored at Day 29. Analysis will be based on intention to treat including all randomized patients. Patients who have received at least four doses of study drug will be considered in a sensitivity analysis for this secondary outcome.

2) Duration of events (e.g., mechanical ventilation or days in the ICU) will be summarized with median and interquartile rage by the study arms and compared between the treatment arms by Wilcoxon's rank sum test or log-rank test.

3) Binary events (e.g., need for intubation) will be summarized as percentages and 95% confidence intervals by the study arms and compared between the treatment arms by Fisher's exact test.

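### Secondary endpoint 13 counts DVT/PE only during the hospital stay, so its window depends on a post-randomisation outcome and omits clots after discharge, including those on home study drug

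*Combined protocol and SAP*

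**What the plan says.** Section 3 and the synopsis (1.1) word endpoint 13 identically: "Clinically relevant deep vein thrombosis (DVT) or pulmonary embolism (PE) [entire hospitalization". No other section widens the window or defines it for readmissions, although 6.1.2.4 expects some patients to be readmitted before Day 14.

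Treatment and follow-up both run past discharge. Section 4.1 states "If patients improve and are discharged prior to day 14 the study drug will be continued until day 14 as an outpatient" (6.1.1 agrees), and "Subjects will be assessed daily while hospitalized and followed until day 60". Discharged patients on study drug are telephoned daily until Day 15, and all patients have contacts at Days 15, 22, 29 and 60 (1.3, 4.1, 8.3).

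Length of stay is an outcome in its own right, endpoint 5: "Days of hospitalization". The other clinical event endpoints in section 3 mostly have fixed windows: SAEs to Day 29, grade 3-4 AEs to Day 60, mortality at Days 14 and 28.

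The analysis section has no entry specific to DVT/PE. The nearest rule, item 3 of 9.3.3, reads "Binary events (e.g., need for intubation) will be summarized as percentages and 95% confidence intervals by the study arms", with Fisher's exact test between arms. It makes no allowance for time at risk or competing events. Separately, 8.4.4 puts grade 3-4 AEs and "all SAEs occurring from the time the informed consent is signed through the Day 60 visit" into the research database.

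**The concern.** Less immunothrombosis is one of the trial's stated hypotheses: section 2.3.3 refers to "inflammatory driven immunothrombosis that precedes much of the organ failure". Endpoint 13 is the only clinical endpoint specific to thrombosis. A patient discharged on Day 6 who has a PE on Day 11, still taking study drug at home, is outside the window, or inside it only if a readmission is taken to count. A patient kept until Day 25 is observed for about four times as long.

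Section 2.3.2 raises the possibility that the drug shortens the disease course. If it does, it also shortens the period in which clots are counted, and a comparison of simple percentages would credit some of that to an effect on clotting. A drug that prolonged stay would be penalised in the same way. Early deaths also shorten the observed stay. Section 9.1 looks ahead to confirmatory studies, so a distorted estimate could be carried forward.

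**Working it through.** The plan gives no clot rate, length of stay or power for this endpoint, so there is no figure of its own to reproduce. From the documents: about 60 patients, 1:1 (9.1), hence about 30 per arm; Day 29 is 28 days after Day 1. All clot hazards and stays below are assumptions. Stays are counted from Day 1, and the clot hazard is identical in both arms throughout, so there is no drug effect on clotting.

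**1. Fixed stays.** In-hospital risk = 1 − exp(−h·L), with daily hazard h and stay L.

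| h per day | L = 8 | L = 12 | Ratio |
|---|---|---|---|
| 0.003 | 1 − exp(−0.024) = 2.4% | 1 − exp(−0.036) = 3.5% | 0.67 |
| 0.005 | 1 − exp(−0.040) = 3.9% | 1 − exp(−0.060) = 5.8% | 0.67 |
| 0.010 | 1 − exp(−0.080) = 7.7% | 1 − exp(−0.120) = 11.3% | 0.68 |

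With 10 versus 12 days the ratio is 0.84; with 8 versus 14 days it is 0.58-0.59.

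**2. Variable stays.** Let time to discharge be exponential with rate μ = 1/(mean stay), and λ = −ln(1 − p)/10, where p is the 10-day clot risk. Then P(in-hospital clot by Day 60) = λ/(λ+μ) × [1 − exp(−60(λ+μ))]. For p = 10%, λ = 0.01054. Mean stay 7 gives 0.01054/0.15339 ≈ 6.9%; mean stay 10 gives 0.01054/0.11054 ≈ 9.5%; ratio 0.72.

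| p | Mean stay 7 | Mean stay 10 | Ratio |
|---|---|---|---|
| 5% | 3.5% | 4.9% | 0.71 |
| 10% | 6.9% | 9.5% | 0.72 |
| 20% | 13.5% | 18.2% | 0.74 |

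Across the same values of p, 8 versus 10 days gives 0.81-0.83, 7 versus 14 gives 0.52-0.57, and equal stays give 1.00.

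**3. How much of this is artefact.** Compare with a count to Day 29 in or out of hospital, for mean stays of 7 versus 10 days and p = 10%. With outpatient hazard λ₂ and H = 28, risk = 1 − exp(−(λ+μ)H) − μ·exp(−λ₂H)·[1 − exp(−kH)]/k, where k = λ + μ − λ₂. The in-hospital ratio is 0.72 in every row.

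| Hazard after discharge | Count to Day 29 | Ratio |
|---|---|---|
| Same as in hospital | 25.5% vs 25.5% | 1.00 |
| One quarter | 11.9% vs 13.6% | 0.88 |
| Zero | (ratio only) | 0.74 |

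The gap between 0.72 and the ratio in the last column is what the window creates. It is large when risk persists after discharge and almost nil when risk stops at the hospital door.

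**4. Effect on a test.** For 30 per arm, two-sided Fisher's exact test at an assumed 5% level (the plan states none): 7 versus 10 days at p = 10% gives 30 × 6.9% ≈ 2.1 versus 30 × 9.5% ≈ 2.9 expected clots. The rejection rate is 1.0%, against 0.9% when both stays are 10 days. The highest rate in the scenarios run was 9.7% (7 versus 14 days, p = 20%).

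**The case against.** A reader might infer that post-discharge clots are lost to the trial. They are not. A PE that is life-threatening or leads to readmission is an SAE under 8.4.2. It is recorded to Day 60 under 8.4.4, counts in the primary endpoint if it occurs by Day 29, and appears in the summaries and listings of 9.3.4. What is missing is its place in endpoint 13. Also at risk are post-discharge clots that are neither serious nor grade 3-4, because 8.4.4 leaves other AEs in the medical records, and concomitant medications are collected only through discharge (6.5).

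A reader might also infer that the arm discharged sooner will show fewer clots. That is an expectation under two conditions, a difference in stay and continuing risk after discharge, and the documents give figures for neither. With only a few clots per arm, chance could hide or reverse it.

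Two further readings go beyond the text. The first is that clots present before Day 1 would count: 8.4.4 treats conditions present before the first dose as baseline for AE reporting, and endpoint 13 simply does not repeat the rule. The second is that Fisher's test is specified for DVT/PE: item 3 of 9.3.3 is the likelier reading, but it names intubation as its example, and item 4 offers Kaplan-Meier and log-rank for time-to-event endpoints.

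Finally, an inpatient window has a merit, since ascertainment is daily and more uniform in hospital. This is also one of thirteen secondary endpoints in a study sized by feasibility, and no stated decision rests on it. All of this limits the size of the point. None of it supplies a reason to let the window vary with an outcome.

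**Conclusion.** The point holds in a limited form. Endpoint 13 uses a window set by a post-randomisation outcome, omits clots after discharge, including those during home dosing, and leaves readmission undefined. Under equal constant hazard in and out of hospital, 8 versus 12 days of stay gives an apparent risk ratio of about 0.67-0.68 with no drug effect; 7 versus 10 mean days under exponential discharge gives 0.71-0.74. These figures rest on assumed hazards and stays. They overstate the artefact if risk falls after discharge, because part of the difference is then a real consequence of leaving hospital sooner. The harm is to the estimate of the only thrombosis-specific clinical endpoint; a significant result from the window alone would be rare at about 30 per arm. This is worth a cheap improvement and does not threaten the trial's primary conclusion.

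**What to change.** - Define endpoint 13 as new DVT or PE with onset from first dose through Day 29, in or out of hospital and including readmissions. Report Day 60 as supportive and keep the in-hospital count as supplementary.
- State that death without a clot is a competing event, and name the analysis method for this endpoint.
- Apply the existing baseline rule of 8.4.4 to clots present before the first dose.
- Add a dated DVT/PE question to the daily calls for patients on home drug and to the Day 15, 22, 29 and 60 contacts, so that events below grade 3 are also entered.

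The cost is endpoint wording plus one question at contacts already planned, with some work to confirm clots diagnosed elsewhere. The downside is weaker ascertainment after discharge: contacts may be by telephone or telehealth, the daily calls end at Day 15, and anticoagulant use after discharge would stay unknown unless collection under 6.5 were extended. Some patients will have incomplete windows, and their number should be reported by arm. The change removes bias from uncounted events; it does not, and should not, remove a true reduction in risk from earlier discharge.

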## 4 STUDY DESIGN

### 4.1 OVERALL DESIGN

We intend to study fostamatinib for the treatment of hospitalized patients with COVID-19.

- This will be a multicenter, randomized, double-blind, placebo-controlled, phase 2 trial with the objective to evaluate the safety of fostamatinib compared to matching placebo in COVID-19 patients who are hospitalized with a 5, 6, or 7 on the 8-point ordinal scale.
- The NHLBI will be the Coordinating Center for this multicenter study. All participating sites will enroll and treat subjects as described below. Research labs for exploratory endpoints will be processed at participating sites or shipped to the NIH Clinical Center for processing.
- All study participants will receive standard of care throughout the entire study and then will be randomized to 150 mg of fostamatinib twice a day or placebo for 14 days (total 28 doses).
- Subjects will be assessed daily while hospitalized and followed until day 60. If patients improve and are discharged prior to day 14 the study drug will be continued until day 14 as an outpatient. Patients who are discharged on study drug will receive a phone call daily to assess for adverse events and will have safety labs drawn on days 3, 5, 8, 11 as applicable (outpatient third party lab acquisition may be utilized as needed). We will make every effort to bring back discharged patients for outpatient visits on days 15, 22, 29, and 60 to include laboratory draws. In patients who are unable to follow-up, they will receive a telephone visit as a follow up.
- Day 1 of study is the first day of study drug and patients will be followed until day 60.

### 8-point ordinal scale for secondary endpoint of efficacy and stratification (World Health Organization 2020)

Scale	Description
8	Death
7	Hospitalized, receiving invasive mechanical ventilation or extracorporeal membrane oxygenation (ECMO)

6	Hospitalized, requiring noninvasive ventilation or use of high-flow oxygen devices
5	Hospitalized, requiring any supplemental oxygen
4	Hospitalized, not requiring supplemental oxygen but requiring ongoing medical care (COVID-19–related or other medical conditions)
3	Hospitalized, not requiring supplemental oxygen and no longer requiring ongoing medical care (used if hospitalization was extended for infection-control reasons)
2	Not hospitalized, limitation of activities, home oxygen requirement, or both
1	Not hospitalized, no limitations of activities

**Standard of Care:**

For the purposes of this study standard of care is defined primarily as remdesivir as an antiviral intended to decrease viral load and dexamethasone a broad-spectrum anti-inflammatory intended to dampen the immune response to SARS-CoV-2. However, it is noted that in the middle of a pandemic evidence for and against specific therapies for the treatment of COVID-19 continue to evolve and therefore standard of care may change throughout this study. At the current time once enrolled, use of any biologic therapy outside of local standard of care are prohibited. This includes monoclonal antibodies targeting cytokines (e.g., TNF inhibitors; interleukin-1[IL-1], IL-6 [tocilizumab or sarilumab]), or T-cells (e.g., abatacept); monoclonal antibodies targeting B-cells (e.g., rituximab in the last 6 months, and including any targeting multiple cell lines including B-cells); JAK inhibitor(s) other than baricitinib (e.g., imatibib, genfinitib); and interferon, plasma, or immunoglobulin (IgG) therapies for COVID-19 are not permitted. However, if patient has a clinical deterioration while on fostamatinib rescue therapies above including convalescent plasma may be considered. Additionally, if a specific site has a change in their standard of care outside of remdesivir and dexamethasone these medications will be permitted.

This study is randomized placebo-controlled study. All patients will receive standard of care described above.

